7.2.3 Primary objective analyses

Primary endpoint analyses in Phase II

The primary endpoint of Phase II is defined in Section 2.1.2.

Viral load data will be log-transformed prior to analysis. Time-weighted average change in log₁₀ viral load from baseline is defined as:

$$\frac{\sum_{i=a}^{b-1} \{0.5 * (Y_i + Y_{i+1}) * (t_{i+1} - t_i)\}}{(t_b - t_a)}$$

Boehringer Ingelheim		
BI Trial No.: 1487-0001		20 Apr 2021
c33563257-02	Clinical Trial Protocol	Page 87 of 127

• Where

- a = baseline assessment at Day 1
- b = last assessment at or prior to the threshold day (Day 8 for the primary endpoint)
- Y_i = change from baseline in log₁₀ viral load at visit i (and where $Y_a=0$)
- t = time at the specified time point (the actual study day)

An analysis of covariance (ANCOVA) model with log_{10} baseline viral load and baseline serology status as covariates will be used. Adjusted means and 95% confidence intervals (CIs) will be provided by treatment group. The ratio of the mean time-weighted change from baseline in log_{10} viral load will be used to quantify the treatment effect, comparing each active treatment arm to placebo as the reference. Intercurrent events will be handled using the Primary strategy as defined in Section 7.2.2.

Primary endpoint analyses in Phase III

The primary endpoint of Phase III is defined in Section 2.1.2.

The cumulative proportion of patients hospitalized or dying by Day 29 will be estimated for each randomised group using Kaplan-Meier (KM) methods to take account of losses to follow-up. It will be estimated overall and within each stratum. The analysis will be stratified by "high" versus "low" risk of progression to severe COVID-19 and baseline serology status.

For patients with known event of hospitalization or death:

Time to hospitalization or death [days] = earlier date of hospitalization or death – date of randomisation + 1.

For patients with no known event of hospitalization or death or where censoring rules apply:

Time to hospitalization or death [days] = date of censoring – date of randomisation + 1.

Missing data are handled by using survival analysis techniques. Intercurrent events will be handled using the Primary strategy as defined in Section 7.2.2. For further details on censoring rules of the primary analysis, refer to Table 7.3.1:1.

At each interim analysis and the final analysis, the two-sided asymptotic 95% repeated confidence interval for the difference in the KM hospitalization or death probability estimate by Day 29 will be found within each stratum. Repeated confidence intervals will be derived as described in (R20-3707).

Since the observations in the two treatment groups are independent, the variance of the Kaplan-Meier probability difference is equal to the sum of the Kaplan Meier probabilities' variances found by Greenwood's method.

Boehringer Ingelheim		
BI Trial No.: 1487-0001		20 Apr 2021
c33563257-02	Clinical Trial Protocol	Page 88 of 127

The difference in the Kaplan-Meier estimates by Day 29 overall will be calculated as the weighted average of the estimated Kaplan-Meier probability differences within each stratum. The weights will be defined as the "Mantel-Haenszel" weights, using the derivation as described in Greenland and Robins (R09-1299). The variance for the overall risk difference will be calculated accordingly. The two-sided asymptotic 95% repeated confidence interval for the Kaplan-Meier probability differences will be shown overall and within each stratum.

One sided p-values will be obtained from a z-test and will be compared with the O'Brien and Fleming local nominal alpha levels.

Proprietary confidential information © 2021 Boehringer Ingelheim International GmbH or one or more of its affiliated companies

7.2.4 Secondary objective analyses

No key secondary endpoints have been defined for this study.

Secondary endpoints are defined in Section 2.1.3.

Time-weighted change from baseline endpoints will be analysed as described in Section 7.2.3 for the Phase II primary endpoint.

Endpoints relating to the occurrence of a certain event by Day 29 (such as Hospitalization by Day 29, Hypoxia or hospitalization or death from any cause by Day 29, Hypoxia by Day 29) will be analysed as described in Section 7.2.3 for the Phase III primary endpoint.

For binary endpoints, comparisons between treatment groups will be performed using a logistic regression model adjusting for the binary covariate baseline serology status. For binary endpoints that are not based on viral load data, "high" versus "low" risk of progression to severe COVID-19 will also be included in the model as a covariate. A likelihood-ratio test will be performed to evaluate the differences between treatments. Adjusted odds ratios together with 95% confidence intervals will be used to quantify the effect of treatment, comparing each active treatment arm to placebo as the reference.

For time-to-event endpoints, a Cox proportional-hazards model will be used to derive the hazard ratio and 95 % confidence interval (CI) of the active treatment regimens versus placebo. The model will include baseline serology status as covariate. For endpoints that are not based on viral load data, "high" versus "low" risk of progression to severe COVID-19 will also be included in the model as a covariate. Breslow's method for handling ties will be used. A log-rank test will be used to evaluate the effect of each active treatment arm compared to Placebo. Kaplan-Meier plots by treatment group will also be presented. The cumulative proportion of patients presenting an event will be estimated for each treatment group using Kaplan-Meier methods. For those endpoints where a sufficient number of events can be observed to calculate the median time-to-event, the median and the corresponding 95% CI using Greenwood variance that is incorporated into the Brookmeyer and Crowley method (R09-6372) with a loglog transformation will be provided for each treatment group.

Any p-values presented for the secondary endpoints will be considered nominal in nature and no adjustment for multiplicity will be made. Two-sided p-values will be provided.

Proprietary confidential information © 2021 Boehringer Ingelheim International GmbH or one or more of its affiliated companies

The strategy for handling of intercurrent events will be specified in the TSAP for secondary endpoints.

20 Apr 2021

33563257-02Clinical Trial ProtocolPage 91 of 127Proprietary confidential information © 2021 Boehringer Ingelheim International GmbH or one or more of its affiliated companies

Proprietary confidential information © 2021 Boehringer Ingelheim International GmbH or one or more of its affiliated companies

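### The loss-of-detection models in protocol 7.2.4 omit baseline viral load, and Breslow ties pull the Phase III Cox hazard ratio modestly toward 1

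*Protocol*

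**What the plan says.** Protocol 7.2.4 sets the models for the secondary endpoints.

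- **Binary endpoints** (Phase II: loss of detection at Days 4, 8, 15, 22 and 29): "For binary endpoints, comparisons between treatment groups will be performed using a logistic regression model adjusting for the binary covariate baseline serology status". Risk group is added only where the endpoint is not derived from viral load, so serology is the only covariate here. The test is stated as: "A likelihood-ratio test will be performed to evaluate the differences between treatments".
- **Time-to-event endpoints** (Phase III: time to loss of detection over 29 days): a Cox model, of which the protocol says "The model will include baseline serology status as covariate". Risk group is again excluded for viral-load endpoints. On ties: "Breslow's method for handling ties will be used". The test is separate: "A log-rank test will be used to evaluate the effect of each active treatment arm compared to Placebo".
- **Time-weighted viral endpoints**: "Time-weighted change from baseline endpoints will be analysed as described in Section 7.2.3 for the Phase II primary endpoint". That analysis, in 7.2.3, is an ANCOVA in which log10 "baseline viral load and baseline serology status as covariates will be used".

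The covariate is available. Flow Chart footnote 13 has the Day 1 swab taken before dosing, and 5.1.1 says that centrally analysed baseline load is used for analysis. Secondary p-values are nominal (7.2.4). The SAP covers Phase II only and, with five patients randomised, replaces all models by descriptive statistics (SAP Sections 3 and 4).

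**The concern.** Endpoints read from the same nasopharyngeal swabs are adjusted differently, and the readable text gives no reason. How much virus a patient starts with may well predict when it becomes undetectable. Protocol 1.1 reports, for another antibody product, enhanced clearance in patients who were seronegative or had high baseline load. That makes load a plausible covariate, although it does not establish how prognostic load is. If load is prognostic, leaving it out costs some power in the small Phase II comparison and changes which odds or hazard ratio is estimated.

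Separately, clearance is seen only when a swab is taken. About 1300 Phase III patients, swabbed at about five visits, share few distinct event days. Breslow's approximation is known to shrink the log hazard ratio when ties are heavy. What is at stake is the reported effect size and its interval, not the test.

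**Working it through.** **1. Covariates side by side (visible text)**

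| Endpoint | Phase | Model | Baseline covariates |
|---|---|---|---|
| Time-weighted change, 8 and 29 days | II | ANCOVA | log10 load, serology |
| Loss of detection by day | II | logistic | serology |
| Time to loss of detection | III | Cox | serology |

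**2. The plan's own figures.** None is given for these models. The nearest is 641 per group for 80% power on the Phase III primary endpoint (7.5.2). Recomputed with Lan-DeMets O'Brien-Fleming bounds at thirds, power is 78.3% to 82.8%, depending on scale and on whether futility stops are followed. It does not depend on this point.

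**3. Phase II logistic model.** From the protocol: 50 per arm (7.5.1). Assumed, because the documents give nothing: conditional treatment odds ratio (OR) 3, placebo clearance 31–35%, serology OR 2, standard-normal load independent of serology.

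logit P(cleared) = a + log 3 × treatment + log 2 × serology + log(OR per SD) × load

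The test statistic is 2(ℓ with treatment − ℓ without), on 1 degree of freedom. There were 3000 trials per row; Monte Carlo error is at most √(0.25/3000) ≈ 0.9 point.

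| OR per SD of load | Power, serology only | Power, load added | SE of log OR, without → with | OR, serology only |
|---|---|---|---|---|
| 1.0 | 77% | 77% | 0.436 → 0.441 | 3.10 |
| 0.7 | 74% | 75% | 0.435 → 0.448 | 3.00 |
| 0.5 | 69% | 72% | 0.431 → 0.465 | 2.81 |
| 0.35 | 62% | 70% | 0.428 → 0.492 | 2.56 |

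With load in the model the estimated OR is 3.13–3.28. Power rises although the SE rises because the conditional effect grows faster. In the last row, log(2.56)/0.428 = 2.20 without load; with load the ratio is between log(3.13)/0.492 = 2.32 and log(3.28)/0.492 = 2.41. Type I error is similar either way: 5.2–6.7% without load, 5.3–6.4% with it.

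A separate set of runs gave gains of 1.4, 4.9 and 8.5 points at OR per SD 0.7, 0.5 and 0.35 under independence. The gains were 0.9, 3.4 and 6.9 if load is 1 SD lower in seropositive patients, and 0.2, 2.5 and 4.0 if it is 1.5 SD lower.

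**4. Phase III Cox model, covariate.** 1300/2 = 650 per arm (7.5.2), Efron ties, actual swab days, assumed median clearance 10 days, hazard ratio (HR) per SD of load 0.8, 0.7 and 0.6. A true HR of 1.5 is estimated as 1.46, 1.44 and 1.40 without load and 1.48 with it. A true HR of 1.2 gives 1.19, 1.18 and 1.17 without load and 1.19–1.20 with it. The SE is unchanged (for example 0.0592 both ways).

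**5. Phase III Cox model, ties.** Swabs at Days 4, 8, 15, 22 and 29, with windows of ±1, 1, 2, 4 and 4 days (Flow Chart). Assumed: exponential clearance from Day 1, serology HR 1.3 with 25% positive, actual swab day as event time; 1000 trials per setting. For d events on one day, with risk-set sum S and tied-case sum D, Breslow uses S^d in the denominator; Efron uses the product over k = 0,…,d−1 of (S − (k/d)D). There are 38–47 events per distinct day.

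| True HR 1.5, median clearance | Breslow (95% CI coverage) | Efron (coverage) |
|---|---|---|
| 7 days | 1.43 (87%) | 1.47 (94%) |
| 10 days | 1.45 (90%) | 1.48 (94%) |
| 14 days | 1.45 (94%) | 1.48 (97%) |

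A separate set of runs gave 1.43–1.47 for Breslow and 1.48–1.50 for Efron, so the sets agree to within about 0.02. On the log scale, Breslow at 1.43 loses 1 − log(1.43)/log(1.5) = 12%, and at 1.47 it loses 5%. At a true HR of 1.2, Breslow gives 1.18–1.19 (coverage 95–96%) and Efron 1.19–1.20.

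For time to death, with daily dates and about 1% events (assumed), the Breslow limit for a true HR of 0.5 is 0.500. The issue is therefore confined to endpoints read at visits.

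**The case against.** The strongest reply is that nothing here is invalid. Under randomisation the serology-adjusted odds or hazard ratio is a legitimate summary, and Breslow errs toward no effect. The log-rank test, Kaplan-Meier curves and medians do not use the tie method, and the p-values are nominal. All of that stands. A reader might infer that the planned analysis is biased by the missing covariate; it is not. It answers a less conditional question.

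The contrast with the ANCOVA is also weaker than it looks. Its outcome is change from baseline, so baseline load belongs there almost by construction, and the 7.2.4 rule for viral endpoints looks deliberate. The case therefore rests on power and on a clear estimand rather than on inconsistency alone.

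Three further inferences are not supported:

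- **That only these endpoints lack the covariate.** Parts of the protocol are redacted, and 7.3.1 mentions a mixed model that no visible section specifies. A hidden endpoint or sensitivity analysis cannot be excluded.
- **That the power gain is around 12 points.** That needs an odds ratio per SD of 0.25 and load independent of serology. The documents give neither figure, and correlation between the two reduces the gain.
- **That Breslow's bias is large because all events fall on five nominal days.** 7.2.4 gives no event-time rule, but 7.2.3 times the Phase III primary endpoint from calendar dates and the time-weighted endpoint by actual study day. Actual days are the natural reading.

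One cost objection holds. The set in SAP 7.5.2.2 requires a measurable baseline load, so the covariate loses nobody there. Phase III analyses include every randomised patient (7.2.1), with no such requirement.

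**Conclusion.** A minor but real specification point. Among the visible viral endpoints, the two loss-of-detection models omit a pre-dose covariate that the trial collects and uses elsewhere. Adding it would raise Phase II likelihood-ratio power by about 0 to 9 points over odds ratios per SD of 1.0 to 0.35 if load and serology are independent, or about 0 to 7 points if seropositive patients have 1 SD lower load. The log odds ratio has a somewhat larger standard error, and the estimate becomes load-conditional.

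Breslow understates a true Phase III hazard ratio of 1.5 as about 1.43–1.47 on actual swab days, against about 1.48–1.50 with Efron. Interval coverage falls below nominal mainly when clearance is fast. At 1.2 the difference is negligible. Efron does not remove all the attenuation, since clearance is still seen only at visits.

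All clearance rates, effects and prognostic strengths are assumptions. A reader might infer that reported results are affected. They are not: the final SAP fits no models and covers no Phase III analysis.

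**What to change.** In protocol 7.2.4:

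1. Add log10 baseline viral load, next to serology, to the logistic model for loss of detection and the Cox model for time to loss of detection.
2. For Phase III, state how missing or undetectable baseline load enters the model, so that all randomised patients are kept. SAP Section 5 already assigns values to results below the quantification limit and to undetectable results, and these could be carried over. Missing values need their own rule, set without reference to treatment.
3. Replace Breslow with Efron for time-to-event endpoints assessed at visits. By the same logic this includes time to clinical improvement. Leave the log-rank test as it is.

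The cost is a few specification lines, with no new samples and no multiplicity consequence. The estimates must be described as conditional on baseline load, and the standard error of the Phase II log odds ratio will be slightly larger.

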7.2.6 Safety analyses

Adverse events will be coded using the Medical Dictionary for Drug Regulatory Activities (MedDRA). Standard BI summary tables and listings will be produced. All adverse events with an onset between start of treatment and end of the REP, a period of 90 days after the last dose of trial medication, will be assigned to the on-treatment period for evaluation.

All treated patients will be included in the safety analysis. In general, safety analyses will be descriptive in nature and will be based on BI standards. No hypothesis testing is planned.

Statistical analysis and reporting of adverse events will concentrate on treatment-emergent adverse events, i.e. all adverse events occurring between start of treatment and end of the REP. Adverse events that start before first drug intake and deteriorate under treatment will also be considered as 'treatment-emergent'.

Frequency, severity (as graded according to DAIDS Table 5.2.6.1.5:1 [R21-0379]), and causal relationship of adverse events will be tabulated by system organ class and preferred term after coding according to the current version of the Medical Dictionary for Drug Regulatory Activities (MedDRA) at database lock.

Laboratory data will be analysed both quantitatively as well as qualitatively. The latter will be done via comparison of laboratory data to their reference ranges. Values outside the reference range as well as values defined as clinically relevant will be summarised. Treatment groups will be compared descriptively with regard to distribution parameters as well as with regard to frequency and percentage of patients with abnormal values or clinically relevant abnormal values.

Vital signs, physical examinations, or other safety-relevant data observed at screening, baseline, during the course of the trial and at the end-of-trial evaluation will be assessed with regard to possible changes compared to findings before start of treatment.

7.2.7 Other Analyses

This section is not applicable.

Boehringer Ingelheim		
BI Trial No.: 1487-0001		20 Apr 2021
c33563257-02	Clinical Trial Protocol	Page 93 of 127

7.2.8 Interim Analyses

In Phase II, an unblinded interim analysis will take place after all patients have completed one week of follow-up. This interim analysis will be performed by the sponsor. The purpose of this exploratory interim analysis is to perform an evaluation of the pharmacological activity by looking at viral load data over time from all patients of this Phase II part. If the drug does not have the expected effect on viral load, no effect on clinical endpoints can be expected. In this case, the trial will be stopped after the exploratory Phase II part. Otherwise, the confirmatory Phase III part of the trial will be started. One active treatment arm will be kept in Phase III depending on data collected and evaluated in the Phase II part. Data from patients included in the Phase II part of the trial will not be used for any confirmatory analyses.

In Phase III, two interim analyses are planned: a first interim analysis is planned after approximately 33% of patients have been followed up for 28 days. The second interim analysis is planned after approximately 67% of patients have been followed up for 28 days. Depending on the primary endpoint results based on the data available at the time of the interim analyses, the decision will be taken to either continue the trial or to stop the trial, either for efficacy or for futility.

If the trial claims for early efficacy at the first interim analysis the recruitment will continue until a total of 650 patients are included in the Phase III part of the trial. At the point of claiming for early efficacy at the first interim analysis the placebo arm will stop recruitment. Both interim analyses in the Phase III will be performed by a DMC and only the DMC will get access to unblinded data.

The DMC will also review data on a regular basis during Phase II and Phase III.

7.3 HANDLING OF MISSING DATA

7.3.1 Efficacy endpoints

For the analysis of the primary endpoint of Phase II and of other continuous endpoints, missing data will not be imputed. For continuous endpoints analysed using a MMRM, the mixed effect model will handle missing data based on a likelihood method under the "missing at random assumption".

For the analysis of the primary endpoint of the Phase III and of other time-to-event endpoints or endpoints assessing the occurrence of an event by a pre-defined timepoint, missing or incomplete data will not be imputed but will be handled using standard survival analysis techniques (i.e. censoring). For the primary analysis of the primary endpoint the censoring rules are outlined in Table 7.3.1:1.

Proprietary confidential information © 2021 Boehringer Ingelheim International GmbH or one or more of its affiliated companies

Table 7.3.1: 1Censoring Rules for the primary analysis of the primary endpoint of
Phase III

Rule #	Situation	Outcome (event or censored)	Date of event or censoring
1	Patient has been hospitalized or has died within the first 29 days and date of hospitalization or death is known	Event	Date of event
2	Patient has been hospitalized or has died within the first 29 days and date of hospitalization or death is unknown	Event	Imputed date of event: 1 day after the date of last contact when the patient is known to be alive and not hospitalized
3	Patient is alive and has not been hospitalized within the first 29 days	Censored	Day 29
4	Patient is alive and has not been hospitalized within the first 29 days but has started within the first 29 days another drug with a similar mode of action as study treatment that has proven efficacy (either preliminary via EUA by FDA or via full approval by the FDA or EMA).	Censored	Start date of drug with similar mode of action
5	Unknown	Censored	Date of last contact when the patient is known to be alive and not hospitalized

Censoring rules for secondary or

further endpoints will also be provided in the TSAP.

For the analysis of the categorical endpoints, missing data will be imputed using the worst

case. Further details will be provided in the TSAP. For further endpoints, handling of missing data will be described in the TSAP.

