The Phase III part of the trial will aim to confirm efficacy, safety and tolerability of the dose regimen of BI 767551 selected from the Phase II part in comparison to placebo in non-hospitalized patients with mild to moderate COVID-19 symptoms. The primary objective is to demonstrate superiority of the BI 767551 dose regimen for the difference in the proportion of patients hospitalized or death from any cause over 29 days. The primary treatment comparison will be performed on all randomised patients, including all data prior to start of any other treatment with a similar mode of action that has proven efficacy (either preliminary via EUA by FDA or via full approval by the FDA or EMA).

Secondary objectives of Phase III are to numerically compare the BI 767551 dose regimen to placebo for virological and other clinical outcomes.
2.1.2 **Primary endpoint(s)**

The primary endpoint in Phase II is the time-weighted change from baseline in viral shedding over 8 days in site collected nasopharyngeal (NP) swabs by RT-qPCR, defined as a change from baseline in \log_{10} viral load. Refer to Section 7.2.3 for further details.

The primary endpoint in Phase III is hospitalization or death from any cause by Day 29.

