7.2.2 Handling of Intercurrent Events

The expected intercurrent events of interest in this trial are:

- Start of a product with a similar mode of action as trial medication that has proven efficacy (either preliminary via EUA by FDA or via full approval by the FDA or EMA)
- Start of a restricted medication as defined in Table 4.2.2.1:1, except any product with a similar mode of action as trial medication that has proven efficacy (either preliminary via EUA by FDA or via full approval by the FDA or EMA)
- Death

The strategies for handling intercurrent events in this trial are as follows:

Primary strategy: This is the effect of randomising a patient to a treatment, but excluding the effects of any other products with a similar mode of action as trial medication that have proven efficacy (either preliminary via EUA by FDA or via full approval by the FDA or EMA). Start of a restricted medication as defined in Table 4.2.2.1:1, except any product with a similar mode of action as trial medication that has proven efficacy (either preliminary via EUA by FDA or via full approval by the FDA or Via full approval by the FDA or EMA) will be handled using the treatment policy approach as defined in ICH E9(R1). Death will be handled using the composite approach as defined in ICH E9(R1). The use of any other products with a similar mode of action as trial medication that have proven efficacy will be handled using the while-on-treatment approach as defined in ICH E9(R1), with the treatment period defined as the period from first administration of randomised medication to the end of the residual effect period or to the start of the intercurrent event, whichever occurs first.

Secondary strategy: This strategy is similar to the primary strategy, except for the intercurrent event "use of any other products with a similar mode of action as trial medication that have

Boehringer Ingelheim		
BI Trial No.: 1487-0001		20 Apr 2021
c33563257-02	Clinical Trial Protocol	Page 86 of 127

proven efficacy (either preliminary via EUA by FDA or via full approval by the FDA or EMA)", which will be handled using the composite approach as defined in ICH E9(R1).

Table 7.2.2:1 provides an overview of the handling of intercurrent events within the different strategies.

Intercurrent Event	Strategy for handling of intercurrent events	
	Primary strategy	Secondary strategy

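### The Phase III censoring table contradicts the stated while-on-treatment strategy: whether a patient is censored when another proven product starts depends on whether a hospitalisation follows

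*Protocol*

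**What the plan says.** Below, the other product means another product with a similar mode of action and proven efficacy, by FDA emergency authorisation or by full FDA or EMA approval.

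- **Objective (Protocol 2.1.1).** The Phase III primary comparison covers all randomised patients, "including all data prior to start of any other treatment with a similar mode of action that has proven efficacy".
- **Strategy (Protocol 7.2.2 and Table 7.2.2:1).** Under the Primary strategy, starting the other product is handled as while-on-treatment, and the period ends at that start. Death is handled as composite. Other restricted medication is handled as treatment policy.
- **Analysis (Protocol 7.2.3).** For the Phase III primary endpoint: "Missing data are handled by using survival analysis techniques. Intercurrent events will be handled using the Primary strategy as defined in Section 7.2.2". The section then refers to Table 7.3.1:1 for the censoring rules. The censored-time formula applies "For patients with no known event of hospitalization or death or where censoring rules apply".
- **Events (Table 7.3.1:1, Rules 1 and 2).** Rule 1 reads: "Patient has been hospitalized or has died within the first 29 days and date of hospitalization or death is known". This is an event on its date. Rule 2 is the same with an unknown date. Neither makes an exception for an earlier start of the other product.
- **Censoring (Table 7.3.1:1, Rule 4).** Censoring at the start date is limited to this case: "Patient is alive and has not been hospitalized within the first 29 days but has started within the first 29 days another drug".
- **Effect measure (Protocol 7.2.3).** "The difference in the Kaplan-Meier estimates by Day 29 overall will be calculated as the weighted average" of the stratum differences, so the scale is the risk difference. The Synopsis describes a comparison of log proportions.
- **TSAP, Section 3.** It covers Phase II only, so it gives no other Phase III rule.

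**The concern.** Take two identical patients who start the other product on Day 4. One is hospitalised on Day 9 and is an event on Day 9. The other is never hospitalised and leaves the risk set on Day 4. The same action on Day 4 gives different handling, decided by what happens afterwards. Kaplan-Meier requires each day's risk set to be fixed without knowledge of the future.

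The result matches neither coherent estimand. It is not while-on-treatment, because hospitalisations after the start count. It is not treatment policy, because event-free starters are removed from the denominator.

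This is the single endpoint under alpha control. One programmer working from Sections 2.1.1 and 7.2.2 and another working from the table would code it differently. The situation is foreseen: Table 4.2.2.1:1, footnote 3, leaves room for other SARS-CoV-2 antibodies as rescue, and Section 3.3.4 keeps patients who take a prohibited treatment in follow-up, so later hospitalisations would be recorded.

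**Working it through.** **1. The plan's own figure, for context.** Section 7.5.2 gives 641 per group for 80% power, 7.5% v 3.75%, one-sided 2.5%, two interim looks. For a fixed design:

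n = [1.960·√(2·0.05625·0.94375) + 0.842·√(0.075·0.925 + 0.0375·0.9625)]² / 0.0375² = 592 per group.

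With Lan-DeMets O'Brien-Fleming bounds at 33/67/100% (z = 3.731, 2.504, 1.994) and the Synopsis futility limits (5% and 10% relative reduction) treated as binding, 641 per group gives 79.7% (pooled), 79.9% (unpooled) or 78.2% (log scale). The 80% is reproduced within 2 points and is not in dispute.

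**2. Hand example.** Let N be the arm size, s the starters before the event day, e all events and e_s the events among starters. With all events on one later day, the Kaplan-Meier risk is:

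- table as written: e / [N − (s − e_s)]
- every starter censored at the start: (e − e_s) / (N − s)
- all events to Day 29: e / N

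Assume N = 650, s = 65 starting on Day 4, e = 49 hospitalised on Day 9 (about 7.5%) and e_s = 5:

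- as written: 49 / (650 − 60) = 49/590 = 8.3%
- every starter censored: 44/585 = 7.5%
- all events: 49/650 = 7.5%

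The two coherent analyses agree here and the table matches neither.

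**3. Simulated risk difference.** True risks without the other product are 7.5% and 3.75%, a difference of 3.75 points. Assumptions: event day gamma (shape 2, scale 4), rounded up and capped at Day 29; start day uniform on Days 2 to 7; a start counts only if it precedes the event; 2,000,000 patients per arm (about ±0.05 points). In the *rescue* scenario, starters have three times the risk and the other product halves later events; this is closest to the documents. In the *neutral* scenario, starts are unrelated to prognosis and the product has no effect. Use is equal in both arms at 10/20/30%:

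| Scenario | As written | Every starter censored | All events |
|---|---|---|---|
| Rescue | 3.6 / 3.6 / 3.7 | 3.3 / 3.0 / 2.8 | 3.4 / 3.2 / 3.0 |
| Neutral | 4.0 / 4.3 / 4.7 | 3.7–3.8 | 3.7–3.8 |

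Placebo risk as written is 7.3/7.3/7.5% (rescue) and 8.0/8.7/9.5% (neutral), against a true 7.5%. The rescue result lies near 3.75 only because selective censoring and the other product's effect offset each other.

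A second simulation with exponential times, 20% use on placebo, 5% on active and an unchanged hazard after the start gave a placebo risk of 8.34% as written and 7.50% with every starter censored. The relative reduction was 53.9% against 50.0%.

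**4. Type I error and power.** 10,000 trials of 650 per arm; looks at 217/433/650 per arm (z = 3.710, 2.511, 1.993); four assumed strata (40% high risk at three times the risk, 25% seropositive at half); Mantel-Haenszel weights, Greenwood variance, no futility stop.

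- Type I error as written, equal use of 10% or 20%: 2.6% (rescue), 2.6–2.7% (neutral).
- Type I error as written, placebo/active use 10/5, 20/10, 30/10%: 1.9/2.6/2.8% (rescue), 3.4/6.0/12.6% (neutral).
- Power, rescue, equal 20% use: 78% as written, 70% with every starter censored, 79% with all events.

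Monte Carlo error is about ±0.3 points near 2.5%, ±0.7 near 12% and ±0.9 for power.

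**The case against.** The strongest reply concerns size.

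- **The neutral scenario fits the trigger poorly.** Rule 4 applies only to products with proven efficacy, yet the neutral scenario assumes no effect. With non-prognostic starts and a product that halves later events, the differences at 10/20/30% equal use fall to 3.87/4.06/4.25. Type I error at 10/5, 20/10 and 30/10% use falls to about 3.1/3.8/6.1% (single look, unstratified). This stands; the distortion shrinks but does not vanish.
- **Use may be rare.** Other antibodies are barred to Day 29 apart from rescue. At equal use of 2% and 5% the differences are 3.70 and 3.68 (rescue), and 3.78 and 3.88 (neutral). In the equal-use runs the relative reduction stayed at about 49–50%. This also stands.
- **Unequal use under the null is unlikely.** Blinding works against it unless the study drug changes rescue use without changing hospitalisation. This stands, so inflated type I error is not the main argument.
- **It may be a drafting slip.** The Section 7.2.3 wording "For patients with no known event of hospitalization or death or where censoring rules apply" suggests that censoring was meant to override a known event. But the only rule for this situation, Rule 4, excludes patients with an event, so the table still has to be corrected.
- **Deaths may be intended to count.** Death has its own composite strategy. This is accepted; the contradiction is clear for hospitalisations only.

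None of these replies reconciles Rules 1, 2 and 4 with the stated strategy.

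**Conclusion.** The concern holds. The contradiction rests on the text and needs no assumption: the primary strategy stops at the start of the other product, while the table counts hospitalisations after it and censors only starters who remain event-free.

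The numerical effect depends on usage rates and prognosis that the documents do not give. With equal use, the Section 7.2.3 risk difference may be nearly unchanged (rescue) or inflated by up to about 1 point at 30% use (neutral: 4.7 against 3.75), and type I error is about nominal. Clear inflation of type I error needs use that differs by arm under the null, and it is largest when the other product has no effect.

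The case for change is agreement between table and strategy, not better operating characteristics. It should be fixed because it concerns the confirmatory primary analysis. The study was discontinued on 25 June 2021 with 5 patients randomised (TSAP Section 4), so this is a defect of the plan and affects no reported result.

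**What to change.** Make the table and the strategy agree, in one of two ways.

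**Option 1: keep while-on-treatment.**
- Rules 1 and 2 count hospitalisations only before the other product starts.
- Rule 4 censors at the start date every patient who starts before an event, whatever happens later, including those with unknown status afterwards. Rule 3 excludes starters.
- Add a rule for a start and a hospitalisation on the same day.
- State how deaths after the start are handled. Counting them while censoring survivors at the start would recreate the same dependence on outcome.
- Also report all events to Day 29 regardless of the other product, unless this is already planned in text not shown in the public version.

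The cost is three or four table rows and one extra run. The statistical price is informative censoring, because starters are likely to be worsening. With starters at three times the risk and 20% use, a true 7.5% is estimated as about 6.0%. In the rescue scenario power is 70% against 78% as written at equal 20% use, and 60% against 79% with 20% use on placebo and 10% on active.

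**Option 2: declare treatment policy for this event in Phase III and drop Rule 4.** Sections 2.1.1 and 7.2.2 must be reworded to match, for Phase III only, because the Phase II primary endpoint uses the same Primary strategy. The estimate then includes the other product's effect (3.2 instead of 3.75 points in the rescue scenario at 20% use).

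Neither option needs new data, since these patients stay in follow-up under Section 3.3.4.
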